## 12.1. Definitions and Classification of Adverse Events

Medtronic uses the definitions provided in ISO 14155:2011 and 21 CFR 812 for AE definitions. Where the definition indicates "device", it refers to any device used in the study. This might be the device under investigation, or any market released component of the system. Medtronic follows MEDDEV 2.7/3 revision 3 guidelines for classifying causality levels; but will apply these causality definitions across all events, not only serious adverse events and definitions have been adapted accordingly.

1. **Severe Hypoglycemia** is an event requiring assistance of another person due to altered consciousness to actively administer carbohydrate, glucagon, or other resuscitative actions. This means that the subject was impaired cognitively to the point that he/she was unable to treat his or her self, was unable to verbalize his or her needs, and was incoherent, disoriented and/or combative.

These episodes may be associated with sufficient neuroglycopenia to induce seizure or coma. Plasma glucose measurements may not be available during such an event, but neurological recovery attributable to the restoration of plasma glucose to normal is considered sufficient evidence that the event was induced by a low plasma glucose concentration. (**Adapted from American Diabetes Association Workgroup on Hypoglycemia, Diabetes Care 28:1245-1249, 2005**)

2. **Severe Hyperglycemia** is defined as hyperglycemia (blood glucose greater than ( $>$ )300 mg/dL) (16.7 mmol/L) with blood glucose ketones greater than ( $>$ )1.5 mmol/L, urine ketones moderate or large, or accompanied by symptoms of nausea, vomiting or abdominal pain.
3. **Diabetic Ketoacidosis/DKA** diagnostic criteria: blood glucose greater than ( $>$ ) 250 mg/dL (or greater than ( $>$ ) 13.9 mmol/L), arterial pH less than ( $<$ ) 7.3, bicarbonate less than ( $<$ )15mEq/L, moderate ketonuria or ketonemia and requiring treatment within a health care facility. (**American Diabetes Association-Diabetes Care, Volume 27, Supplement 1, January 2004; S94-S102**)

Hyperglycemic events will be recorded as DKA if the event includes the presence of all of the following:

- Arterial blood pH less than ( $<$ ) 7.30 or serum bicarbonate less than ( $<$ ) 15mEq/L
- Blood glucose greater than ( $>$ ) 250 mg/dL (or greater than ( $>$ ) 13.9 mmol/L)
- Serum ketones or large/moderate urine ketones
- Symptoms such as polyuria, polydipsia, nausea, or vomiting
- Treatment provided in a health care facility

## Adverse Event (AE) (ISO 14155-2011)

Any untoward medical occurrence, unintended disease or injury, or untoward clinical signs (including abnormal laboratory findings) in subjects, users or other persons, whether or not related to the investigational medical device.

**Note 1:** This definition includes events related to the investigational medical device or the comparator.

**Note 2:** This definition includes events related to the procedures involved.

**Note 3:** For users or other persons, this definition is restricted to events related to investigational medical devices.

## Adverse Device Effect (ADE) (ISO 14155-2011)

Adverse event related to the use of an investigational medical device.

Note 1: This definition includes adverse events resulting from insufficient or inadequate instructions for use, deployment, implantation, installation, or operation, or any malfunction of the investigational medical device.

Note 2: This definition includes any event resulting from use error or from intentional misuse of the investigational medical device.

## Serious Adverse Event (SAE) (ISO 14155-2011)

Adverse event that:

- a) Led to a death,
- b) Led to a serious deterioration in the health of the subject, that either resulted in
  1. a life-threatening illness or injury, or
  2. a permanent impairment of a body structure or a body function, or
  3. in-patient or prolonged hospitalization, or
  4. medical or surgical intervention to prevent life-threatening illness or injury or permanent impairment to a body structure or a body function,
- c) Led to foetal distress, foetal death or a congenital abnormality or birth defect

**Note:** Planned hospitalization for a pre-existing condition, or a procedure required by the CIP, without serious deterioration in health, is not considered a serious adverse event.

*\*For the purpose of this study, Inpatient Hospitalization is defined as: admission to the hospital for a period of 24 hours or more based on urgent medical need rather than elective admission.*

For the purpose of this study, the term "life-threatening" in the definition of "serious" refers to an event in which the patient was at risk of death at the time of the event; it does not refer to an event which hypothetically might have caused death if it were more severe. (ICH Topic E 2 A Clinical Safety Data Management: Definitions & Standards for Expedited Reporting. EMEA 2006)

## **Serious Adverse Device Effect (SADE) (ISO 14155-2011)**

Adverse device effect that has resulted in any of the consequences characteristic of a serious adverse event

## **Unanticipated Adverse Device Effect (UADE) (21 CFR 812.3(s))**

Any serious adverse effect on health or safety or any life-threatening problem or death caused by, or associated with, a device, if that effect, problem, or death was not previously identified in nature, severity, or degree of incidence in the investigational plan or application (including a supplementary plan or application), or any other unanticipated serious problem associated with a device that relates to the rights, safety, or welfare of subjects.

## **12.2. Reporting of Adverse Events**

The Investigator or designee will record ALL AEs while the subject is enrolled in the clinical study. Each AE needs to be assessed for its device or procedure relatedness. A device related AE is associated with the use of the study device (e.g. infection of sensor site or infusion set occlusion resulting in DKA). A procedure related AE is associated with testing related to the study procedures specified in the CIP (e.g. IV insertion pain, FST exercise injuries). This includes study procedures such as FST and lab draws.

Examples of device or procedure related AEs include:

- **Device related (ADE):** insertion site infection
- **Serious adverse device effect (SADE):** cellulitis at device insertion site requiring hospitalization
- **Procedure related AE:** bruising at IV insertion site

Subjects participating in the study have diabetes and are expected to experience hypoglycemia and or hyperglycemia. These normal events are not expected to be reported to sponsor on an AE eCRF as this is not considered an untoward event, but rather an expected occurrence. Any glycemic excursion that meets the protocol definition of Severe Hypoglycemia, Severe Hyperglycemia, or DKA is considered an untoward event and a worsening from the subject's baseline and would be reported to sponsor on an AE eCRF.

Baseline medical conditions should only be reported to sponsor on an AE eCRF if there is a worsening from the subject's baseline. For example, a subject previously diagnosed with Asthma is hospitalized for severe asthma attack would be a reportable event.

Adverse events will be documented in the subject source file and reported to sponsor on an eCRF. The investigational center is responsible for documentation of AEs including obtaining source documents related to the event, such as emergency medical technician/paramedic reports, hospital records (admission summary; lab results, test results, discharge summary) or device uploads to support the event. Source documents will be reviewed to determine if additional AEs have occurred and require reporting.

Adverse events that have not resolved at the time of the subject's discontinuation or completion of the study should have an "outcome" of Not Recovered/Not Resolved at study end in subject source and on an eCRF. The investigator should ensure that subject is aware of any follow-up or additional treatment that is required for any ongoing AE at EOS participation; however, there will be no eCRF entry for the ongoing follow-up.

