**FST Timing for 14-80 years old:**

Group	Sensor Wear Day	Timing of YSI™* FST & Start of Challenge (if applicable) from Sensor Insertion T=0
A1	Day 1, 3, 4 and 7	2-10 hours (+2), 50-58 hours (±6), 74-82 hours (±6), 146-154 hours (±6)
A2	Day 1, 3, 4 and 7	10-18 hours (±2), 58-66 hours (±6), 82-90 hours (±6), 154-162 hours (±6)
B1	Day 1, 3, 4 and 7	18-26 hours (±2), 66-74 hours (±6), 90-98 hours (±6), 162-170 hours (-6, +2)
B2	Day 2, 4, 5 and 6	24-32 hours (±2), 74-82 hours (±6), 98-106 hours (±6), 122-130 hours (±6)
C1	Day 2, 4, 5 and 6	32-40 hours (±2), 82-90 hours (±6), 106-114 hours (±6), 130-138 hours (±6)
C2	Day 2, 4, 5 and 6	40-48 hours (±2), 90-98 hours (±6), 114-122 (±6), 138-146 hours (±6)

Subjects will be assigned to the following sensor location and FST schedule:

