#### **Start of Study Period: To be completed in 60 days from Visit 4 to Visit 12; Additional 15 days for sensor replacements (e.g. 75 days)**

- Visit 4: Phone Visit or Optional Office Visit
  - **Group A1**- May be combined with Visit 5 (e.g., if sensor insertion for Day 1 is done at Visit 5)
  - **Group A2,B1, B2, C1 and C2**-Investigational center must confirm that the Guardian™ Sensor (3) insertion was performed at the appropriate insertion time, insertion location, and SMBG reminder.
- Visit 5: YSI™\* 1st FST
- Visit 6: Follow Up Phone Call
- Visit 7: YSI™\* 2nd FST
- Visit 8: Follow Up Phone Call
- Visit 9: YSI™\* 3rd FST
- Visit 10: Follow Up Phone Call
- Visit 11: YSI™\* 4th FST
- Visit 12: End of Study Visit
  - Subject has worn sensors for T= 176-188 hours.
  - Visit 11 and Visit 12 may be combined (e.g., FST occurs on day 7 and end of the sensor wear)

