#### **8.2.2.8. Visit 12: End of Study**

- Visit 11 and Visit 12 may be combined. (e.g., FST occurs on day 7 and end of the sensor wear).
- Investigational center staff will ensure sensor wear time has been met (T=176-188 hours) and the sensor may be removed at that time. It is recommended to have subject remove sensor at clinic to ensure it is removed at proper time.
- Subjects will return to the clinic to address any questions, concerns, and collect adverse events or device deficiencies.
- For subjects who are still wearing the Guardian™ Sensor (3)(s), instruct subjects to remove them
- Upload study devices via:
  - CareLink™ Personal For Clinical Research software (CONTOUR®NEXT LINK 2.4 study meter)
  - GST Download Utility Software (Guardian™ Connect Transmitter) following instructions provided
- Perform a Skin assessment on the area of each of the Guardian™ Sensor (3) insertion sites and document in subject source and complete the Skin Assessment eCRFs

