# CIP324 Clinical Investigation Plan

10838519DOC

Version H

Page 82 of 173

Medtronic

- Return all study sensors, devices, unused supplies and study guides from subjects (refer to Section 6.4)
- An Exit eCRF will be completed at this visit.

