# CIP324 Clinical Investigation Plan

10838519DOC

Version H

Page 126 of 173

Medtronic

	

Reduction of IV fluid if subject shows signs of CHF, lower extremity edema, crackles on lung auscultation or S3 heart sound

 
Subjects who still exhibit signs of fluid overload at time of discharge will be transported to the emergency room (ER) or follow guidelines of the local institution for the disposition of subject.

Risks with hyperglycemic challenges	Prevention and Mitigation 
Risks with hyperglycemia may include:
 

Diabetic ketoacidosis

Symptomatic ketosis

Cardiovascular event

Dehydration

Potassium and sodium imbalance

Shock

Altered mental status

Coma

Acidosis

 
Prevention and Mitigation include:
 

Follow frequent blood sampling per protocol (See Section 10.5.1)

Clear guidelines for management during hyperglycemic challenge

IV access to give immediate insulin

Qualified investigator presence during experiment

Stopping challenge procedures if ketones are elevated or subject is exhibiting signs and symptoms of DKA (Please refer to the ketone management guidelines in the protocol)

Limiting the time the subject is allowed to stay in the hyperglycemic ranges

The subject is under constant observation and monitoring at all times during the challenges

Preventing subjects who do not have a carb/insulin ratio and insulin sensitivity factor from participating in the challenge (observational only)

Investigational centers are to use glucose meter in the event a FST blood glucose value is not available at the required time interval.

Follow the Ketone management instructions per protocol

 
Treatment of these risks include:
 

IV fluid administration with 0.9 NS will at a rate of 100 cc per hour if ketonemia develops

Rescue therapy management treatment guidelines are provided in the protocol for hyperglycemic events

IV insulin administration will be per the institutions DKA protocol if DKA is suspected

Immediate withdrawal from study if subject is exhibiting signs and symptoms of DKA (Stop the challenge, stop the FST and DO NOT continue with any future scheduled frequent sampling days).

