# CIP324 Clinical Investigation Plan

10838519DOC

Version H

Page 127 of 173

Medtronic

	

Transfer to ER or follow DKA guidelines of the local institution for the disposition of subject if subject is exhibiting signs and symptoms of DKA

Risks with hypoglycemic challenges	Prevention and Mitigation
Risks for hypoglycemia may include: 

Seizure

Coma

Altered mental status

Loss of consciousness

Cardiovascular event

Death

Risk of rebound hyperglycemia with ketosis

	
Prevention and Mitigation include:
 

Follow frequent blood sampling per protocol (See Section 10.5.1)

Clear guidelines for management during hypoglycemic challenge

IV access to give immediate dextrose or other emergency drugs

Qualified investigator presence during experiment.

Limiting the time the subject is allowed to stay in the hypoglycemic ranges

The subject is under constant observation and monitoring at all times during the challenges

Preventing subjects who do not have a carb/insulin ratio from participating in the challenge (observational only)

Investigational centers are to use glucose meter in the event a YSI blood glucose value is not available at the required time interval.

 
Treatment of these risks include:
 

Rescue therapy treatment instructions are provided in the Hypoglycemic and Hyperglycemic Challenge Guidelines

IV administration of dextrose if uncooperative orally with food or liquid

Glucagon if subject does not respond to Dextrose

Immediate withdrawal from study if severe hypoglycemia (stop the challenge, stop the FST and DO NOT continue with any future scheduled frequent sampling days)

 
Transfer to ER or follow severe hypoglycemia guidelines of the local institution for the disposition of subject.

---

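### Section 12.2 bars eCRF follow-up after exit without excepting serious events, so the AE eCRF cannot tell later recovery from death or lasting harm when such an event is ongoing at exit

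*Protocol*

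**What the plan says.** Protocol Section 12.2 has sites record all AEs while a subject is enrolled. An AE that has not resolved at discontinuation or completion is coded Not Recovered/Not Resolved, both in source and on an eCRF. The investigator makes the subject aware of any further care needed, but "there will be no eCRF entry for the ongoing follow-up". The rule applies to any ongoing AE.

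The same section makes the site responsible for source documents that support an event, including hospital records and the discharge summary. The introduction to Section 12 lists the end date and outcome among the facts to document for each AE.

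Section 10.9 withdraws any subject who has DKA, unconsciousness or severe hypoglycemia. Section 11.1, under hyperglycemic challenges, calls for "Immediate withdrawal from study if subject is exhibiting signs and symptoms of DKA", and also "Transfer to ER or follow DKA guidelines of the local institution for the disposition of subject". Under hypoglycemic challenges it likewise calls for immediate withdrawal after severe hypoglycemia.

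SAP Section 7.9.12 plans a descriptive summary of all adverse events and specifies no outcome table.

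**The concern.** For most AEs, a data cut-off at the end of participation is an ordinary choice. It fits less well here because some of the gravest events end participation themselves. A subject withdrawn for DKA and sent to an emergency room may have exited before anyone knows how the episode ends.

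If so, the AE eCRF keeps one outcome for very different courses: full recovery, lasting injury or death. Section 11.4 gives the glucose challenges as the reason the study is classed as significant risk. Whether a challenge-related DKA resolved is therefore a question the sponsor should be able to answer from its own database. At stake is the completeness of the descriptive safety record; no hypothesis test is involved.

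**Working it through.** No arithmetic applies, and the plan states no figure to reproduce. The check is a reading of the relevant sections side by side.

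**Step 1. Does the rule cover serious events?** Section 12.2 is worded for any ongoing AE and does not distinguish by seriousness, relatedness or event type. It does.

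**Step 2. Is there an exception elsewhere?** I looked in protocol Sections 10.9, 10.10, 12.1 to 12.8, 13.1, 14 and 17.9.2, and in SAP 7.9.12. The nearest candidates do other jobs:

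| Section | What it does | Does it update the outcome after exit? |
|---|---|---|
| 12.3 | Prompt first notification of severe hypoglycemia, DKA, SAE and SADE, with details known at the time | No |
| 12.4 | Deadline for the UADE report | No |
| 12.5 | Makes records used for the causality review available to the sponsor | No |
| 13.1 | CEC review of classification and causality | No |
| SAP 7.9.12 | Descriptive summary | No |

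I found no exception.

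**Step 3. Can a subject exit with such an event unresolved?** Section 10.9 ties withdrawal to the event itself. Section 11.1 places withdrawal alongside transfer for acute care. No section makes exit wait for resolution. Exit before the outcome is known is therefore possible, though not scheduled.

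**Step 4. Do the data used for analysis hold the answer by another route?** Section 10.7 says that data required for analysis are captured on eCRFs. The discharge summary is a source document. Section 12.2 has the site obtain it but does not direct its content back to the AE eCRF after exit.

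**Result.** For an SAE, SADE, DKA or severe hypoglycemia ongoing at exit, the site is to obtain records that may show the outcome, while the eCRF stays at Not Recovered/Not Resolved.

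**The case against.** The strongest reply is that this is a disclosed cut-off and that little is lost.

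- The code is true as of exit.
- The protocol does not date exit after withdrawal, so a site that holds exit open until recovery can code the event as resolved.
- Hospital records are obtained and the sponsor has access to them. The CEC reviews SAEs, SADEs, DKA and severe hypoglycemia.
- Death and permanent impairment are SAE criteria, so they are captured as far as they are known by exit.
- Sections 10.7 and 17.3.4 provide for queries. The eCRF completion instructions and the Data Management Plan are not among the documents and might allow a later correction.
- A discharge summary gives status at discharge and may not show whether harm lasts.
- Using records after withdrawal depends on consent and HIPAA wording supplied under separate cover.

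Most of this stands, and it keeps the point at low severity. It does not remove it. Section 12.2 as written rules out the eCRF entry, and a query process that allowed it would contradict that text. The last two items limit the remedy: it should ask for no follow-up beyond the records already due, and only where the authorization covers them.

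**Conclusion.** The point holds as a low-severity, cheap improvement. Section 12.2 has no serious-event exception, and withdrawal triggered by DKA or severe hypoglycemia can put exit ahead of the outcome. The number of affected events cannot be estimated from the documents and is probably very small. Severe hypoglycemia would usually resolve before exit; that is an assumption, since the documents give no durations. The accuracy endpoints, stopping rules, seriousness coding and CEC review are unaffected.

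Two stronger readings are tempting, and the documents support neither.

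**Normal completion cutting across an admission.** A reader might compare a late last session, such as "162-170 hours (-6, +2" in group B1, with the end-of-study condition "Subject has worn sensors for T= 176-188 hours". Section 12.1 limits inpatient stays to an "admission to the hospital for a period of 24 hours or more based on urgent medical need rather than elective admission", so the reader might infer that a subject admitted after the last session would be exited mid-admission. But 176 hours is a minimum wear time, and Section 8.1 lets sensors come off then or later. Exit is tied to attendance: Section 8.2.2.8 says "Subjects will return to the clinic to address any questions, concerns, and collect adverse events or device deficiencies" and "An Exit eCRF will be completed at this visit". A subject in hospital cannot attend, and Section 8.2.2.1 allows 60 days from Visit 4 to Visit 12. The timing does not show exit during an admission.

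**Sizing the problem from planned enrollment.** A reader might treat the excess of the 460 enrolled over the 244 completers as subjects exposed to this gap. Under Section 7.2 enrollment begins at consent, so the excess includes screen failures and subjects who leave after the training period. It says nothing about how many have a serious event ongoing at exit.

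**What to change.** Add one sentence to Section 12.2:

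*For SAEs, SADEs, DKA and severe hypoglycemia ongoing at exit, the AE eCRF outcome and end date are updated from the hospital or discharge records the site obtains under this section, up to the final data verification (Section 17.3.3).*

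These are the four event types that Section 12.3 already singles out for prompt reporting. Require no follow-up beyond those records, and keep the present rule for all other AEs.

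The change needs no new visit or staff. Its cost is that sites update a few AE eCRFs after exit, provided the consent and HIPAA authorization cover those records.

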## 12.3. Notification of Adverse Events

### Sponsor Notification:

As soon as possible (desired within 24 hours of investigator or study coordinator awareness), the investigational center staff must report all Severe Hypoglycemia, DKA, SAE, and SADE to Medtronic. For the previously mentioned events, the AE eCRF will be completed with all known details as soon as possible, this will serve as notification to Medtronic. If the study database cannot be accessed due to technical problems, contact the sponsor via email at [[contact]](mailto:[contact]) and provide the known details of the event. Once the access issue has been corrected, the event should be entered onto an AE eCRF.

## 12.4. Expedited Safety Reporting Requirements

For device studies, investigators are required to submit a report of a UADE to the sponsor and the reviewing IRB as soon as possible, but in no event later than 10 working days after the investigator first learns of the event (812.150(a)(1)).

The sponsor will notify the investigator and IRB of any event that results in a safety report per regulations to the FDA. Documentation of IRB notification of any safety event must be kept at the investigational center and a copy sent to the sponsor.

*It is the responsibility of the investigator to follow their IRB reporting requirements.*

